## Version history:

Version	Amendments/Revisions	Date approved
Version 2.0	N/A	

## 1.0 **BACKGROUND AND HYPOTHESES**

There are currently over 3 million breast cancer survivors in the United States, representing approximately 41% of all female cancer survivors. The majority of breast cancer patients will survive their disease and enter into a prolonged survivorship phase of care. Breast cancer patients are at heightened risk for a multitude of physical and psychosocial effects of disease and treatment, including psychological distress (defined as psychiatric morbidity or prevalence of psychiatric disorders, particularly anxiety and depression). Distress is associated with substantial morbidity in breast cancer patients. A recent systematic review concluded that patients who experience breast cancer have higher rates of psychological distress than the general population. Negative effects of distress in breast cancer patients include decreased health-related quality of life, decreased cellular immunity, poorer medication adherence, increased hospitalizations and health care utilization, maladaptive coping, increased symptom burden, delayed return to work, and poorer overall survival. Meta-analyses of psychosocial and medical interventions for breast cancer patients, such as counseling, pharmacotherapy, health education, exercise, and coping skills training, concluded that these techniques can improve psychosocial functioning, health-related quality of life, symptom burden, and emotional well-being.

Unfortunately, it has been shown that identification of distress in breast cancer patients is sub-optimal, leading to increased burden of disease as well as increased strain on our health care system. Cancer patients report that clinicians do not understand their psychosocial needs, and fail to recognize, treat, or offer referral for treatment of distress. In addition, several studies have shown that oncologists substantially underestimate patient psychosocial needs. Prominent oncology organizations such as the American Psychological Oncology Society, Association of Oncology Social Work, and the Oncology Nursing Society now endorse large-scale distress screening programs for cancer patients

However, the effectiveness of systematic distress screening on improved identification of distress, referral for services, and outcomes for breast cancer patients in non-academic settings has not been established. Distress screening programs are not without costs, and the benefits may be limited. Small randomized trials of distress screening have shown modest benefits for cancer patients, typically in improved initiation of referrals; however, observational trials have found only partial, if any, benefit. The impact of distress screening on referral completion, patient-reported outcomes, and utilization of health care services in larger, community-based studies is rarely measured. This raises serious questions about the effectiveness of large scale distress screening programs in non-academic settings, as evidenced in recent literature calling for the need for continued research in this area. Our translational research proposal addresses the gap between efficacy and effectiveness of distress screening..

In addition to the issue of effectiveness, barriers and facilitators to implementation have largely been unaddressed, as well as other critical implementation outcomes such as fidelity, acceptability, or stakeholder-perceived achievements (e.g., successes and failure). To date, a small number of studies show that oncology clinicians and care managers express mixed opinions regarding distress screening programs, with many reporting concerns regarding the acceptability, usefulness, practicality, and sustainability of such programs, and implementation of pilot distress screening programs has not been uniformly successful. Only about half of American College of Surgeons (ACoS) accredited cancer programs report feeling confident that they can implement a distress screening program in their organization. There are significant barriers to successful implementation of distress screening programs, including the acceptability of the program to patients and clinicians and fidelity to the screening program components. Additionally, effective linkages and/or referral pathways to risk-stratified treatment programs are necessary (e.g., documented clinical workflow for referral of patients endorsing severe versus mild distress). Failure to explicitly address these issues may lead to wasteful, unsuccessful programs. Given this context, and the fact that many evidence-based interventions that are shown to have efficacy in controlled trials will fail to translate into meaningful effectiveness in

different settings, it is imperative to conduct rigorous research on effectiveness and implementation of distress screening for breast cancer patients in non-academic settings. We propose to use approaches and tools from the field of dissemination and implementation science (D&I) to provide a robust framework and study design. The rapidly growing field of D&I emphasizes the need for researchers to engage in ongoing evaluation beyond measurement of efficacy from randomized controlled trials, including rigorous assessment of effectiveness (versus efficacy-only studies), as well as study of implementation factors including acceptability and feasibility, context (e.g., processes, systems), and culture (e.g., norms and values). Post-implementation evaluation is integral to the success of translational research. It provides critical insights into the barriers, facilitators, and outcomes associated with the program and lays the groundwork for successful dissemination, scale-up, and spread of effective programs.

## **2.0 OBJECTIVES AND PURPOSE**

This study is a pragmatic cluster-randomized control trial (RCT) to determine the effectiveness of a guideline-recommended distress screening program for breast cancer patients in improving a) identification of distressed patients, b) initiation/completion of referrals to behavioral health, and c) patient-reported and utilization outcomes as compared to usual care within Kaiser Permanente Southern California (KPSC), which is a large integrated health care system serving over 4 million members. We will use a hybrid effectiveness-implementation study design. We will implement and evaluate the effectiveness of the distress screening recommendations (the intervention) from the joint task force of the American Psychosocial Oncology Society, Association of Oncology Social Work, and Oncology Nursing Society, which includes recommendations for the timing of distress screening (e.g., initial visit, timed intervals) designated screening responsibility, distress screening instruments, and referral thresholds. We will use strategies from implementation science to potentially enhance uptake and adoption of the screening intervention.

To achieve our objectives, we propose the following specific aims:

**Aim 1:** Evaluate the effectiveness of a guideline-recommended distress screening program for breast cancer patients in improving identification of distressed patients, initiation and completion of referrals to behavioral health, and patient-reported and utilization outcomes as compared to usual care within KPSC, using a pragmatic cluster randomized control trial design.

**Aim 2:** Identify patient-, clinician-, and system-level barriers and facilitators to implementation of the program, and assess stakeholder-perceived acceptability, fidelity, and achievements of the program.

Note that we are not developing or evaluating a new type of distress screening instrument, or developing/evaluating a new psychosocial intervention/treatment.

## **3.0 STUDY DESIGN**

We will use an effectiveness-implementation hybrid study design that allows for simultaneous study of the clinical effectiveness and implementation of distress screening to address the need for evidence in both areas. Hybrid designs have *a priori* focus on assessing outcomes relevant to both effectiveness of an intervention and implementation-related outcomes. We will employ a sequential mixed methods study design that integrates qualitative and quantitative methods, as is appropriate to address the proposed research questions. Our highly pragmatic approach is guided by the Pragmatic-Explanatory Continuum Indicator Summary-2 with adaptive workflow design. We will use the Consolidated Framework for Implementation Research (CFIR) to guide collection and analysis of implementation outcomes.

[figure not shown]
We will use cluster randomization at the medical center level. There will be 6 KPSC medical centers participating in total: 3 intervention sites and 3 control sites.

The screening program will be implemented at the 3 intervention sites, offering the program to all newly diagnosed breast cancer patients within the intervention site over a 12-month period with no exclusions. Under the intervention condition, distress screening using the Patient Health Questionnaire (PHQ), available in the electronic record, will be offered to patients in clinic (paper-based surveys or completed online with the assistance of the LVN, MA, RN or other member of the clinical team administering the screening). Patients are free to refuse distress screening.

Control condition patients will receive the current standard of care (ad hoc distress screening at the clinician's discretion) and basic education about the study. Control sites will not be prohibited from using the PHQ. We anticipate a total sample of 1,200 newly diagnosed patients, 600 in each arm.

Intervention sites will receive audit and feedback of performance data and implementation facilitation throughout the 12-month intervention period (implementation strategies).

**Figure 1: Pragmatic cluster randomized control trial**

We will collect data from the electronic medical record on screening, initiation and completion of referrals to behavioral health, and utilization outcomes. We will also collect patient-reported outcomes survey data (Aim 1) for patients in both the intervention and control sites (at -3 months, -6 months, -12 months), and will conduct qualitative interviews (n=30) with medical oncologists, breast cancer care coordinators/navigators, social workers, oncology nurses (RNs, LVNs or MAs), clinical leadership and/or patients regarding implementation outcomes (Aim 2).

## 4.0 **STUDY METHODS**

- 4.1 **Implementation strategies:** All sites will have access to the PHQ-9 questionnaire in the electronic health record, information about the study, and basic education on distress screening. Sites randomized to intervention will additionally receive electronic audit and feedback of their site performance (percent of eligible patients offered screening and anonymized comparison to the other sites) and implementation facilitation (a research RN checking in with the sites to troubleshoot, train, and re-configure workflow as needed).
- 4.2 **Identification of participants for screening:** We will identify potential participants at all 6 sites with a new diagnosis of breast cancer using pathology data and appointment/referral data from the KPSC electronic record. We validated our pathology identification algorithm using cancer registry data for recent breast cancer cases diagnosed between 2014 and 2016. Diagnosis is confirmed via chart review and appointment data as needed. All eligible patients will be tracked for screening, referral, utilization, and other outcomes. Eligible patients at intervention sites will be flagged for screening. As this is a highly pragmatic trial, no patients will be individually contacted for recruitment and enrollment as the intervention is applied at the system level; eligible patients will be offered the distress screening program at intervention sites as part of usual clinical care.
- 4.2.1 Secondary chart review to identify potentially benign patients in cohort: In April 2018, we determined that several patients who had scheduled initial consultation visits with medical oncology and were identified by our data algorithm as newly diagnosed breast cancer patients were later determined (through downstream pathology reporting) to not have breast cancer; these are patients who are ultimately determined to have benign hyperplasia. To mitigate this identification issue, we instituted a secondary chart review process to capture these patients and determine them ineligible for the study based on their "benign" status.
- 4.3 **Timing of distress screening:** Eligible patients at intervention sites will be asked to complete the PHQ-9 at their initial visit with the medical oncologist, and encouraged to repeat the screening at follow-up visits with the oncologist.
- 4.4 **Method of screening:** We are using PHQ, a recommended distress screening instrument (the PHQ is available in multiple languages). This instrument has been shown to be a valid, reliable tool with high sensitivity and specificity for measuring distress in the cancer population. The instrument is also credible and acceptable to KPSC clinicians and the PHQ are already built into the KPSC electronic health record. The screening will be offered as part of usual care at the intervention sites. Patients are free to refuse distress screening.
- 4.5 **Adaptive workflow design and responsibility of screening program:** We have developed an adaptive approach to the screening workflow, where the screening process can be completed differently at intervention sites depending on local context and resources. While the timing of the screening (e.g., initial visit, follow-up visit), instrument, scoring, and referral algorithm remains the same across all intervention sites, the type of staff overseeing the screening, screening mode (e.g., on paper, entered into computer), and place of screening during the visit (e.g., while in waiting room, while in exam room) can vary. As recommended in the guidelines, we have identified specific staff embedded in the oncology breast care teams to be the main points of contact for the screening program. These staff include: Oncology Department Administrators (DAs) and Assistant Department Administrators (ADAs), as well as oncology RNs, LVNs, MAs, and social workers where appropriate. Accountability and oversight of screening at each site can

vary per local context. We have provided ongoing training and support to the clinical care teams identified at each intervention site (implementation facilitation).

- 4.6 **Scoring of screening instrument:** We have incorporated a validated KPSC scoring algorithm for the PHQ screening, based on the PHQ scoring instructions, to ensure correct scoring and appropriate referral. Results will group a patient into one of 3 categories: 1) Low score: referral to Health Education (e.g., stress reduction classes, mind/body classes and sleep improvement classes, etc.); 2) Moderate score: referral to Depression Care Management (a program of KPSC Complete Care, see 4.6.1) or local oncology social worker to discuss referrals and individual options; 3) High score: immediate referral to Behavioral Health/psychiatry. In the event of endorsement of suicidal ideation (regardless of overall score), an in-person or telephone consultation with a behavioral health provider will be initiated; escort to behavioral health and/or the emergency department will be decided by the behavioral health provider and medical oncologist. A detailed protocol and training will be provided to all intervention sites.
- 4.6.1 **Complete Care Depression Program.** The Depression program is an integrated, regionally supported program based in primary care and using a population based approach to: 1) identify and treat depression based on evidence and best practices; 2) offer screening and assessment models (i.e. integrated into current care processes); and 3) advance treatment care models (both core and customizable components). The goal of the program is to improve the care of adult patients with co-morbid conditions by the appropriate screening, assessment, and treatment of depression as an extension of Primary Care/Care Management in conjunction with Behavioral Health. Depression Care Specialists provide treatment, including medication initiation and management, education, problem solving treatment and behavioral activation. Under a program redesign, new workflows were developed, which typically begin with the administration of the PHQ.
- 4.7 **Referral pathways:** Per guideline recommendations, we will leverage referral pathways to behavioral health services which may include the oncology social worker (if such a resource is available at the site), depression care managers, and psychiatry/behavioral health. This approach leverages existing resources from the KPSC Complete Care Depression Program.
- 4.8 **Identification of participants for patient-reported outcome surveys.** All eligible patients who speak English or Spanish will be invited to participate in a survey of patient-reported outcomes. We will confirm if the potential participant has an active email address via our membership databases. Those who do will be initially contacted via email; those who do not will be initially contacted via postal mail (see contact workflow descriptions, below). Those who agree to participate will be asked to complete these two brief surveys at 3 time points (3-, 6- and 12-months). We will alert the oncology teams at all participating medical centers, as well as KPSC Member Services, in advance so that they are aware of the survey administration schedule and prepared to address any patient questions about the surveys and/or the study.
- 4.9 **Survey administration and tracking:** We will use RedCap software for all recruitment and survey tracking, as well as for on-line consenting and administration of the surveys whenever possible (e.g., for all patients with a viable email address), as well as for tracking postal mail and phone recruitment contact attempts.
- 4.10 **Outcomes:**

Primary. Our primary outcome is percent of eligible patients screened and referred (based on PHQ score) at intervention versus control sites.

Secondary. Our secondary outcomes include: completion of recommended referrals, utilization of outpatient medical oncology visits, primary care visits, behavioral health visits, urgent care visits, and emergency department visits; we will also examine patient-reported outcomes using the Functional Assessment of Cancer Therapy-Breast survey, and the Breast Cancer Prevention Trial (BCPT) Symptom Checklist.

***Please note: We received a waiver of written informed consent for the electronic health record data collection aspect of the study to identify newly diagnosed breast cancer patients at intervention and control sites during the screening intervention period (12 months) on September 22, 2016; we received a waiver of written informed consent for the survey portion of the study on May 8, 2017.***

## **5.0 DATA SOURCES**

We will obtain and compare data from the sources described below for patients from both the intervention and the control condition.

- 5.1 Distress screening: We will use a recommended distress screening instrument (PHQ), which is part of the electronic health record.
- 5.2 Referral: We will access referral data using Tapestry, a database linked to the KPSC electronic medical record that records all referral activities, including those to behavioral health services. We will collect referral data retrospectively at completion of the 12 month screening intervention. We will collect and compare the number of referrals to relevant behavioral health services, including: depression care management, psychiatry, psychology, social work, and health education. We will also obtain information on referral initiation and completion (e.g., patient visit with referred provider).
- 5.3 Utilization of health care services: To compare patient utilization of health services between intervention and control sites, we will capture utilization of health services from our electronic medical record using Current Procedural Terminology (CPT) and International Classification of Disease (ICD) codes as appropriate. We will collect utilization data retrospectively at 18 months after the initiation of the distress screening program in the intervention centers. This will provide utilization data for a maximum of 18 months. We will capture number of emergency department visits, hospitalizations, urgent care visits, primary care and oncology visits, and behavioral health visits, including interactions with psychology, psychiatry, and social workers (in-person, email, and telephone contact).
- 5.4 Covariates and breast cancer treatment data: We will collect covariate information from the electronic health record and data from the KPSC tumor registry. Covariates from the registry will include date of diagnosis, age at diagnosis, stage of disease, estrogen receptor/progesterone receptor/human epidermal growth factor receptor 2 status, treatment types and dates including use of Herceptin and aromatase inhibitors, laterality, tumor size and histology, sequence number, and treating medical center. Covariates from the electronic record will include age, date of birth, gender, race/ethnicity, and geocoded census tract education and income.
- 5.5 Surveys: We will invite all newly diagnosed breast cancer patients at the intervention and control sites to complete two short patient-reported outcome surveys, the Functional Assessment of Cancer Therapy for Breast Cancer (FACT-B) and the Breast Cancer Prevention Trial Symptom Checklist (BCPT). Those who agree to participate will be asked to complete these two brief surveys at 3 time points (3-, 6- and 12-months).

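### Referral data are to be collected at month 12, when cohort entry ends, so late entrants in both arms have almost no time to complete a referral; Sections 5.2, 12.0 and 14.2 leave this date unreconciled.

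*Combined protocol and SAP*

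**What the plan says.** Section 4.10 makes referral completion a secondary outcome: "Our secondary outcomes include: completion of recommended referrals, utilization of outpatient medical oncology visits", followed by other visit types. Section 5.2 sets the collection time: "We will collect referral data retrospectively at completion of the 12 month screening intervention". It then adds, without a date of its own, "We will also obtain information on referral initiation and completion (e.g., patient visit with referred provider"). The referral destinations it lists are "depression care management, psychiatry, psychology, social work, and health education".

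The entry period is the same 12 months. Section 3.0 offers the program at intervention sites over 12 months, and the consent-waiver note in Section 4.10 describes data collection "to identify newly diagnosed breast cancer patients at intervention and control sites during the screening intervention period (12 months").

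Utilization is dated differently. Section 5.3 says "We will collect utilization data retrospectively at 18 months after the initiation of the distress screening program in the intervention centers" and "This will provide utilization data for a maximum of 18 months". The items it captures include "behavioral health visits, including interactions with psychology, psychiatry, and social workers (in-person, email, and telephone contact").

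Three other places bear on the date. Section 13.2 repeats the referral data source and gives no date. Section 12.0 places the count of behavioral health referrals under its utilization heading, next to behavioral health visits, again undated. Section 14.2 analyses referral and utilization outcomes together, as totals over a study period that it does not define.

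**The concern.** A query run on the day entry closes cannot contain visits that happen afterwards. A patient first seen in month 11 may be screened and referred that day and attend the referred service in month 13. Under Section 5.2 as written, that referral counts as not completed. Referrals made later, for example after the repeat screening encouraged at follow-up visits (Section 4.3), are lost in the same way.

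The completion percentage is a result in its own right. Aim 1 asks whether screening leads to completed referrals, and a low figure would be read as patients or services failing to follow through. Part of it would reflect only the date of the query.

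**Working it through.** **Inputs from the documents.** Entry runs from month 0 to month 12 in both arms (3.0, 4.10). The referral query is at month 12 (5.2) and the utilization query at month 18 (5.3).

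**Inputs assumed.** The documents give neither the entry pattern nor any lag. I take entry as uniform over 12 months and the time from entry to the completed visit as exponential with mean d months.

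**Calendar check.** Potential follow-up is the query month minus the entry month.
- Utilization: 18 − 0 = 18 months for the first entrant, which reproduces the stated maximum; 18 − 12 = 6 months for the last.
- Referral: 12 − 0 = 12 months for the first entrant; 12 − 12 = 0 for the last; mean 6 under uniform entry.

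**Share of eventual completions missed, all entrants.**
- Month 12: (d/12)(1 − e^(−12/d))
- Month 18: (d/12)(e^(−6/d) − e^(−18/d))

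| Mean lag d (months) | Missed at month 12 | Missed at month 18 |
|---|---|---|
| 0.25 | 2.1% | about 0 |
| 0.5 | 4.2% | about 0 |
| 1 | 8.3% | 0.02% |
| 2 | 16.6% | 0.8% |
| 3 | 24.5% | 3.3% |

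For d = 3: (3/12)(1 − e^(−4)) = 0.25 × 0.982 = 0.245 at month 12, and 0.25 × (e^(−2) − e^(−6)) = 0.25 × 0.133 = 0.033 at month 18.

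**Entrants of the last 3 months.** Month 12: (d/3)(1 − e^(−3/d)) gives 32%, 52% and 63% for d = 1, 2 and 3. Month 18: (d/3)(e^(−6/d) − e^(−9/d)) gives 0.1%, 2.6% and 8.6%.

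**If the referral itself also comes late.** Suppose the referral lag and the visit lag each have mean d. The survival function is then e^(−t/d)(1 + t/d). For d = 1 to 3, the month-12 query misses 17% to 47% and the month-18 query 0.2% to 13%.

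**Comparison between arms.** If lags and entry timing are the same in both arms, the same share is lost in each, and the ratio of completion between arms is unchanged by the query date.

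**A fixed 6-month window.** It leaves out e^(−6/d) of completions: 0.2%, 5.0% and 13.5% for d = 1, 2 and 3. With both lags it leaves out 1.7% to 41%. This loss does not depend on when a patient entered, which is the gain over the month-12 query.

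**The case against.** **The date may already be month 18.** Section 12.0 classes the number of referrals as utilization, utilization is collected at month 18, and Section 14.2 treats the two together. In Section 5.2 the dated sentence speaks of referral data, and the sentence on completion carries no date, so applying month 12 to completion is an inference. This stands in part. Section 12.0 gives no date and does not mention completion, so it cannot override the only explicit referral date in the plan. It does mean that the dates are unreconciled and the undercount is not certain.

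**The month-18 extract may already hold the late completions.** The behavioral health list in Section 5.3 is introduced as inclusive. Section 5.2 counts depression care management and health education among relevant behavioral health services, and Section 4.7 also names depression care managers. The extract could therefore cover every destination. What is missing is a sentence saying that its visits count as completed referrals.

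**The lags are assumed and may be short.** True: at 0.25 to 0.5 month the loss is 2% to 4%.

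**A stronger reading: bias in favor of screening.** Control screening is left to the clinician (3.0), so a reader might infer later control referrals. If only control referrals lagged by a mean of 1 to 3 months, with the visit lag equal to it in both arms and equal eventual completion, the month-12 completion ratio would be 1.10 to 1.43 (for example 0.755/0.527 = 1.43), against 1.00 to 1.11 at month 18. Nothing in the documents shows such a difference, and part of any such ratio could be a real benefit of earlier referral.

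**A second stronger reading: utilization totals without person-time are an error.** A reader might infer this from the 6-to-18-month range. The documents do not support it. Section 14.2 leaves the model open, so an offset is not excluded, and unequal exposure shared by both arms mainly adds noise. Nor is a simple offset clearly better. With mean follow-up of 12.5 against 11.5 months, no true effect and front-loaded visits (rate e^(−t/k), k = 12, 6, 3 months), raw totals give ratios of 1.05, 1.03 and 1.01, and a single offset gives 0.97, 0.95 and 0.93. With a constant rate the order reverses: 1.09 for totals, 1.00 for the offset.

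**Conclusion.** The point holds for referral completion. Taken as written, Section 5.2 closes observation when entry closes, and completion is understated for late entrants in both arms. The calendar result (12 months down to about zero) follows from the documents alone. The size does not: 8% to 25% missed rests on uniform entry and mean lags of 1 to 3 months, and falls to 2% to 4% with much shorter lags. Sections 5.2, 12.0 and 14.2 do not agree on the period, so the plan must settle it before anyone can say how much is lost.

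Three inferences go too far: that the comparison between arms is biased, which would need lags or entry timing to differ by arm; that the primary outcome is affected, since intervention patients are screened at the first visit and referred on that score, and no loss there is shown; and that the utilization analysis is wrong. This is a change that should be made to a secondary outcome. It does not threaten the trial's main result.

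**What to change.** 1. In Section 5.2, collect referral initiation and completion together with the month-18 utilization extract. Every patient then has at least 6 months of potential follow-up, less after death or disenrolment.
2. Make Sections 5.2, 12.0 and 14.2 agree on that date, and define the study period in 14.2.
3. State whether a visit to a referred provider found in the month-18 extract counts as a completed referral, and confirm that depression care management and health education are captured.
4. Keep completion of recommended referrals as the outcome. Report it over a stated per-patient window from the first medical oncology visit, for example 6 months, which is available for all entrants. Add a time-to-completion analysis using all follow-up as a companion. Both must account for clustering by site.
5. Optional: a utilization sensitivity analysis over a common 6-month window, or with person-time split by period.

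**Cost.** The referral query runs 6 months later, but no later than Section 5.3 already requires, plus some SAP wording. A 6-month window leaves out slow completions (0.2% to 14% with one lag of 1 to 3 months, more if referrals are also late), which is why the companion is needed. The companion has its own weakness: censoring follows entry date, and intervention sites receive feedback and workflow changes throughout, so late entrants there may differ from early ones.
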